| Domain of Focus | Description of measure & suitability |
|---|---|
| Child behaviour outcomes | |
| Strengths & Difficulties Questionnaire (SDQ) | 25 items, subscales: attention & concentration, conduct problems, emotional problems in children 2-16 years. Widely used across diverse groups, showed sensitivity to change in PuP RCT [16]. Completed by mothers and fathers. |

Brief Infant Toddler Social and Emotional Assessment (BITSEA) 42 items. Widely used, sensitive to change, used for infant 12-36 months.

Child protection outcomes

Brief Child Abuse Potential Inventory (B-CAPI) 33 items, subscales include Abuse Risk plus Lie Scale and Random Responding. Sensitive to presence of abuse, validated for use in mothers on OST and used in PuP RCT [16].

Child Protection data on child involvement

At-risk CP registrations and de-registrations and out-of-home placements - obtained from Social Work Scotland records (with participants' permission).

Parenting knowledge, skills and competence

The Parenting Sense of Competence Scale (PSCS) 17-item self-report scale used to measure satisfaction / comfort with being a parent; parental self-efficacy (i.e. perception of knowledge and skills); and interest in parenting. Widely used in parenting literature and sensitive to change.

Quality of caregiving

Emotional Availability Scales (EAS) 10 minute video recording of parent and child; age appropriate game or activity. Scale draws from attachment theory and emotional availability constructs; has good convergent validity with attachment style as assessed by the *Strange Situation* procedure. Suitable from infancy to late childhood.

Maternal Antenatal Attachment Scale (MAAS)

19-item self-report scale used to measure antenatal maternal attachment and is widely used. Suitable for first-time parents or those without current child care responsibilities during antenatal period. Conducted once at baseline and before EDD.

Paternal Antenatal Attachment Scale (PAAS)

The PAAS is the corresponding measure to the MAAS. 16-item self-report scale used to measure paternal antenatal attachment. It is an accurate predictor of post-birth father-child attachment. Conducted at baseline and before EDD.

Parental affect regulation

The Difficulties in Emotion Regulation Scale (DERS)

36-item scale measuring six dimensions; e.g., lack of awareness of emotional responses, limited access to emotion regulation strategies, difficulties controlling impulses when experiencing negative emotions. Well validated psychometrically and widely used in intervention studies that focus on mindfulness.

Couple Relationship

The Revised Conflict Tactics Scale (CTS2) 39-item scale used to assess the presence and severity of Intimate Partner Violence, sensitive to change. Used by Stover et al. [13] - the only existing study of IPV prevention in substance-abusing men.

Substance use

| | _ |
|------------------------------------|--|
| Treatment Outcome Profile (TOP) | 20 items. Measures substance use, including illicit use in last 28 days, injecting risk behaviour, crime, health and quality of life. Widely used in clinical practice in the UK to measure change and progress in drug treatment. |
| Prescribed OST drugs & daily dose | Objective data to show changes in OST drug type and dosage. Obtained from prescriber (with permission from participants). |
| Health Economics | _ |
| Service Use questionnaire | Bespoke weekly parent-report questionnaire that measures health, social care, and criminal justice service utilisation. |
| EQ-5D-5L | 5-item health related quality of life survey, used in the generation of quality adjusted life years (QALYs) |
| Treatment Fidelity | _ |
| PuP Fidelity Measure | 20-item parent completed measure at end of treatment to assess which components of the PuP programme were covered. |

OST = opioid substitution therapy

Note: all measures to be completed independently by both fathers and mothers in the study.

Observational measure: Improving the quality of the caregiving relationship is a key focus of the PuP programme. The use of video recorded interactions is considered the gold standard for obtaining the best measures of quality of caregiving. In this study we will video record approximately 10 minutes of father (caregiver)-child and mother-child interaction. The parents are simply asked to "be with their child as they usually would". This will be done in the home using a digital recording device. The footage (recorded on encrypted NHS video-recording equipment) is downloaded onto a NHS computer secure drive and is then coded/scored. This method is widely used in family intervention research including the RCT of PuP in the UK [40]. There is no undue participant burden on families over and above self-report measures. The importance of obtaining independent observational data to support self-reported measures of change is key in this project. Mixed methods evaluations where there is convergence between self-report and observational measures provide greater confidence in outcomes. Permission to use and analyse video-recorded data for this study will be obtained from each parent as well as NHS Lothian R&D Office.

Randomisation: Because randomisation will not be evaluated directly in this study, we will assess acceptability of randomisation in a future PuP trial by exploring the concept in qualitative interviews with parents and services. We will ask parents (hypothetically) whether they'd be willing to be randomised in a research evaluation of this intervention. This question will be accompanied by a brief description of what the randomised comparison would be – e.g., randomisation to early vs delayed receipt of the PuP intervention; or randomisation to PuP vs standard care. To explore the feasibility of cluster-randomisation, we will ask a range of service managers whether they'd be willing, in principle, for their service to be randomised to implementing PuP or standard care.

Assessment and follow up

Assessment of families will be conducted at baseline (prior to starting PuP), end-of-treatment (at completion of PuP or at drop-out), and at six months follow-up. In addition, parents recruited into the study during the antenatal period, who are expecting their first child, or who have no current child care responsibilities because their children are not living with them, will complete MAAS & PAAS close to the expected date of delivery (36-40 weeks gestation).

Because assessment of effectiveness is not a study aim, our feasibility assessment is described below.

Assessment of efficacy/effectiveness

Assessing training, the delivery, uptake and engagement with PuP: (Research questions 1-4 are addressed in this section). Between October 2017 and April 2018 qualitative work will be undertaken to better understand the factors that shape the implementation and uptake of PuP. This includes semi-structured interviews with PuP practitioners and recipients of the programme and focus groups with staff from referral agencies. Interviews with PuP practitioners will take place after they have completed the programme with two families. This will offer them greater opportunity to reflect on their experience. Fathers and mothers will be interviewed after they complete, or drop out of the programme. Referrers (e.g., GPs and Addiction treatment staff) will take part in a focus group at the end of the implementation phase to enable them to reflect upon the process of referral, acceptability and delivery of the programme. The interviews and focus groups will be conducted by the Research Fellows in convenient venues for staff. Recruitment data will be recorded by the Research Fellows. Attendance and completion data on each family will be recorded by the PuP practitioners using a specially designed recording sheet.

Analysis: Qualitative data will be analysed iteratively to capture emerging themes and to elicit perspectives on the underlying theory of change which underpins PuP, for example, fathers' ability to improve emotional regulation and the relationship they have with their children. We will also explore barriers and facilitators that affect the implementation and uptake of PuP. For fathers, this includes pragmatic and other events that might prevent/enable engagement with PuP such as time commitments, acceptability or changes to their health, social, criminal justice or family circumstances. For the PuP practitioners we are interested in their perception of the training programme and supervision (including acceptability) and the extent to which PuP becomes embodied within their professional role. We will also examine the extent to which it is embedded in the host organisations (PrePare, CIRCLE, Children 1st, WLDAS) and in the referral pathways from the perspective of staff working in services who refer fathers and families to PuP (e.g. Primary Care and specialist addiction services). The Research Fellows will report on the feasibility of interviewing fathers who drop out of PuP including the practical and ethical issues that need to be addressed and overcome when undertaking this work. Recruitment and attendance data will be analysed to provide uptake and flow rates through the programme.

Assessing recruitment, gathering research data, assessing impact, and a future study: (Research questions 5 – 11 are addressed in this section). Routine data collected by the Research Fellows between May 2017 and October 2018 will provide: detailed quantitative data on participant flow through the study comprising recruitment rates, numbers providing informed consent and numbers completing the outcome measures at baseline, end-or-intervention and at six months follow up. Researcher field notes will provide the reasons for these rates and the best methods of recruiting and retaining participants in the study. We anticipate that we will need to be flexible and dynamic to maximise retention of families, particularly at six months follow-up. All difficulties and solutions (e.g. change of address/mobile phone numbers, use of text messaging and reminders), will be recorded in the final report. At each research interview we will ask families to provide their views on the acceptability and appropriateness of all the measures, including the economic measures, for example, time taken to complete and level of intrusiveness. In addition, we will explore the parent's willingness to provide consent in the future for their routinely collected data to be used in future studies that link data sets to answer questions about long term outcomes.

Although our predominant focus is on questions of feasibility, we will provide an indication of the possible impact of PuP. Analysis of change will include a calculation of the clinical significance of change using the *reliable change index [51]*. The focus will be on measures of parental emotion regulation; emotional availability/antenatal attachment and child abuse potential. Data will be synthesised in the final report and recommendations made as to whether a pilot trial should be conducted and if so, what features should be considered including an economic evaluation. We will use the ADePT process to guide our recommendations [43].

Sample size justification

Our main justification for the sample size of 24 families with a father/male caregiver who is on opioid substitution therapy (OST) is related to the qualitative data collection and analysis requirements, namely:

- 1. This number is large enough to include a purposive sample of families with differing characteristics to reflect diversity within the larger population of families who would likely take part in a larger trial for example: families with concordant parents (where the mother is also drug-dependent) as well as discordant couples; younger and older fathers; first-time and experienced fathers (with more than one child), resident and non-resident fathers; biological and non-biological fathers. We will develop a sampling matrix to guide recruitment to ensure our study sample reflects the wider population of families seen in routine clinical practice. We will also document a socio-demographic profile of the sample to demonstrate the results of our sampling approach.
- 2. This sample size is also small enough to enable an in-depth analysis of the qualitative data (within the time constraints of the study) to inform our research questions around acceptability, barriers and facilitators to implementation and 'usual care' for fathers. We will conduct in-depth interviews with all parents involved in the study, as well as interviews with the PuP practitioners and focus groups with referring clinicians. We anticipate that this qualitative data will result in lengthy transcripts which will provide rich accounts of involvement in the PuP programme and study. A sample size, limited to a maximum of 24 families, will allow the research team to undertake a more detailed and critical comparative analysis of the whole data set.
- 3. This sample size also allows for an attrition rate of approx. 1/3 of families (n=8) without jeopardising the validity and rigour of the study for example, some may withdraw from the study, or drop out of the intervention or fail to complete follow-up measures. In clinical practice, many of these families stop attending services for a variety of reasons (for example, the children are taken into care, the family moves out of the catchment area, imprisonment, illness/hospitalisation etc) and attendance rates are often poor when compared to other families who have less complex needs. Thus, we calculated a desirable number of families (n=16) to complete the PuP programme and 6 month follow-up measures and then added a hypothetical but realistic attrition rate of 1/3rd to arrive at a sample size of 24 families.

Statistical analysis

Quantitative data analysis: Descriptive statistics of routinely collected data, including standard deviation values to inform the sample size calculation of the future trial, will provide a profile of the participants and an estimate of study throughput. This will include: number of eligible fathers approached, number who decline to join the study, enrol, complete and drop-out of PuP. Flow of participants through the screening, intervention and follow-up stages of the study will be summarised in a similar manner to the CONSORT guidance for clinical trial reporting.

Quantitative feasibility outcomes (willingness of participants to be randomised; outcome measure completion rates; up-take, retention and follow-up rates) will be summarised by the number and percentage of participants. Descriptive statistics (number and percentage; or mean, standard deviation, median, lower quartile and upper quartile) will be used to summarise pre-treatment, end-of-treatment and follow-up (6 months after treatment completion for: child behaviour (SDQ, BITSEA), paternal and maternal parenting confidence (PSCS), maternal and paternal antenatal attachment (MAAS/PAAS), couple relationship functioning (CTS2), substance use substance related problems (TOP), prescription data, child protection data, sociodemographic data, child and family health, relationship history and paternity. In addition, changes from pre-treatment to each of the subsequent time points will be reported descriptively.

Clinically significant change measure: We will determine the extent to which individual families made clinically significant change using the Reliable Change Index [51]. This will determine whether there has been a reliable improvement in each of the key domains for both fathers/caregivers and mothers on: parental emotion regulation (DERS); emotional availability (EAS); antenatal attachment (MAAS/PAAS); and child abuse potential (B-CAPI). This measure of individual change is able to provide data on the proportion of fathers and mothers who were able to show a clinically significant improvement, those who showed no change and those who deteriorated.

Health economic assessment: The acceptability of the measures used, in particular the potentially sensitive issues around criminal justice and child protection will be assessed qualitatively. It will also be important to identify if health utility measurement using EQ-5D-5L is felt to be appropriate by this patient group in this context. A dry run conversion of resource use data to generate cost data will be performed by applying standard UK price weights and quality adjusted [45]. A full cost-effectiveness analysis will not be attempted as this would be inappropriate with this sample size. Analysis will instead focus on completeness of returned data, barriers to data collection, acceptability of data collection process and limitations in costing exercise with only summary statistics reported for outcomes.

Qualitative data analysis: Interviews and focus groups will be audio-recorded using an encrypted digital voice recorder, transcribed verbatim, anonymised and entered into NVivo v10 for content coding and thematic analysis. The Research Fellows will anonymise the data and complete the initial content coding, referring to the interview schedules and focus group topic guide for *a priori* issues, but also highlighting emergent topics. Transcripts will be second coded by research team members and initial analytic summaries will focus on participant views, experiences and meanings [53] as well as barriers/facilitators and contextual issues related to the implementation and acceptability of PuP. A constant comparison method [54] and framework analysis [55] will be used to build a matrix of the 'theme' and 'case' analysis, so that they can be mapped onto the logic model and discussed in research team meetings. This will provide a more nuanced and explanatory analysis for discussions on the implications of the findings. A narrative report of the qualitative data results, illustrated with participant quotes and focus group excerpts, will be written up for the final report.

Data Management Plan

All data pertaining to this study will be managed in accordance with The University of Stirling IT security and data protection policies and NHS Lothian IT security and data protection policies in order to ensure that participants' personal identifiable data and anonymised data are fully protected.

This study does not involve storage of any personal identifiable data on University computers nor does it involve the electronic transfer of personal identifiable data from the NHS to the University. Recruitment of participants into the study will involve transfer of patients' names and contact details - this will be done either via telephone or via [name] secure nhs.net email account.

The Research Fellow will record personal identifiable details of participants (e.g. consent forms, personal details sheet) on paper only and these paper records will be kept in a locked cupboard, in a locked room, in a University campus building. The Research Fellow will use a password protected and encrypted University laptop (for use in community treatment sites) to record participant responses to the questionnaires used in this study. All questionnaires will have identifying information (e.g. names, D.O.B) removed and will include only participant unique identifier codes (allocated on enrolment into the study), with the laptop stored in a locked cupboard and locked room in the NMAHP Research Unit, University of Stirling. Access to study data held in the University will be restricted to [name] and the appointed Research Fellows.

Audio-recordings of qualitative research interviews/focus groups with patients and staff will be conducted using an encrypted digital voice recorder. Audio files will be downloaded by the Research PuP4Dads Study PROTOCOL; 11.06.18; v4.0 Page **15** of **22**

Fellows (who conduct the interviews) onto the secure server site at The University of Stirling, transcribed, anonymised and then entered onto NVivo v10, a software package to aid qualitative data analysis. Audio-recordings will be deleted from the voice recorder machine as soon as the file has been downloaded to the secure server. Only fully anonymised transcripts (anonymised by the Research Fellows and checked by [name]) will be made available to the wider research team. Any publications/presentations from this study will include only anonymised excerpts from interviews to ensure participants cannot be identified.

Video recording of parent-child interaction for the observational measure (Emotional Availability Scale - EAS) will be recorded using an encrypted NHS video recording device and downloaded onto a secure NHS shared server site within the Clinical Directorate, accessible only to [name] and [name] (Lead Consultant Clinical Psychologist). [name] will arrange on-site access to the video recordings for the purpose of coding the data (over a two day period at the end of the data collection period) by trained EAS data coders who will obtain a 'letter of access' agreement via NHS Lothian R&D Office. [name]/[name] will approve the nominated EAS data coder and will also code a random 25% sample of the EAS scores.

All personal identifiable data for this study (e.g. consent forms, participant details sheet, audio-files, video files) will be destroyed by [name] within 12 months of the study ending. All non-identifiable data (e.g. questionnaire data, anonymised transcripts) will be held for a maximum of 5 years after the study has ended. [name] will ensure that all data for this study is securely stored/archived and destroyed as described above.

Dissemination

This project is a collaboration between clinicians and researchers to help improve the lives of children and families affected by parental drug misuse. The evaluation places families centre stage and utilises their views and experiences to guide implementation. We will ensure findings are disseminated widely and discussed with key stakeholders including: families involved in the study, Service User Forums, the Study Steering Committee, service providers and managers, commissioners, policymakers, and Alcohol and Drug Partnerships. To this end we will host an expert event for stakeholders, ensuring both adult and child health audiences are included. We will offer further meetings should these be required, for example to help disseminate the intervention into routine practice. In addition to the final report and lay summary we will publish our findings in peer-reviewed journals and present at an international conference.

The research team

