One promising parenting programme for drug-dependent parents, developed in Australia, is the *Parents under Pressure (PuP) programme*. PuP was found to be effective in a randomised controlled trial (RCT) [16] with parents in methadone maintenance treatment and is currently the subject of a multi-centre RCT in the UK [40]. However, these evaluations primarily focus on mothers. Evidence from our review of the literature suggests that there are many challenges to involving fathers, especially high risk fathers with complex needs, in both parenting programmes [41] and research studies [3]. Thus, we need to determine: a) the uptake, retention and acceptability of PUP among drug-dependent fathers (and partners when recruited together); b) acceptability among staff referring into and delivering the programme and; c) critical factors that would affect a future RCT including, gaining informed consent, uptake and participation rates, the feasibility of gathering outcome and cost data from fathers, mothers and staff, and possible sources of contamination.

Research objectives

Aim: To implement and test the feasibility and acceptability of the PARENTS UNDER PRESSURE (PuP) programme for opioid-dependent fathers and their families and to determine whether a future pilot RCT and full scale evaluation including an economic evaluation, could be conducted.

Objectives: By the end of the study (24 months), we will have:

- 1. Determined whether a pilot RCT and full evaluation, including an economic evaluation, could be undertaken on the Parents under Pressure (PuP) programme with drug-dependent fathers and their families.
- 2. Assessed the recruitment and retention of drug-dependent fathers, as well as feasibility, and acceptability of the intervention among fathers, mothers, practitioners, referrers and key services.
- 3. Assessed the fidelity and reach of intervention delivery by PuP practitioners, including barriers and facilitators to successful implementation.

- 4. Refined and tested the logic model and theoretical basis of the intervention.
- 5. Enhanced understanding of the parenting needs of drug-dependent fathers and what programme components work best with fathers.
- 6. Determined key trial design parameters for a possible future large-scale trial, including recruitment and retention rates and strategies, outcome measures, intra-cluster correlation and sample size.

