PART ONE: Will answer research questions 1-4. Firstly, we will estimate the pool of potential fathers in Lothian who are on opioid substitution therapy (OST). Treating clinicians (in Lothian region) will invite eligible fathers to take part in the study, and we will enrol 24 fathers and their families in the PuP programme, thereby providing information on numbers eligible, approached and enrolled in the programme. The intervention will be delivered by twelve accredited PuP practitioners employed by four partner agencies: the City of Edinburgh Council Social Work Department 'PREPARE Team', and the Third Sector Scottish Family Support Service 'CIRCLE', Children 1st (Midlothian) and West Lothian Drug and Alcohol Service (WELDAS). PuP will be provided as an adjunct to 'treatment as usual' health and social care, including individual-based addiction treatment and child protection services. Expert PuP practitioner supervision will be provided by an accredited PuP supervisor, based in Oxford. Treatment fidelity will be monitored by asking parents to complete a bespoke PuP Treatment Experience Measure.

Qualitative interviews with enrolled fathers and mothers before starting PuP will investigate 'treatment as usual' service utilisation, including drug treatment and previous involvement with parenting and family support services. 'Usual care' for drug dependent fathers will also be explored in focus groups with referrers at the end of the implementation phase and with other key stakeholders in our 'expert event' (see below). Interviews with both parents when they complete the programme, or drop out, will explore acceptability of PuP and strategies for successful implementation. Interviews

with PuP practitioners conducted throughout the implementation phase, and focus groups with referring professionals, will explore operational issues and provide an iterative approach to feedback on programme delivery. All interviews and focus groups will be conducted by the Research Fellows and will take place in convenient locations (e.g. community 'recovery hubs' or within participants' homes).

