Finally, self-regulatory skills are developed with children through combined sessions with the caregivers and child/children. These self-regulatory skills again draw from mindfulness constructs with a growing body of evidence supporting the relationship between mindfulness and adaptive emotional regulation [49] particularly for young children with difficulties with emotional regulation. These skills are appropriate for children aged 3-8 years. As parents become more emotionally regulated, they are able to provide more sensitive caregiving. This in turn, is associated with the development of emotional regulation in young children [50]. Thus, the *Parent Workbook* supports the parent by allowing for a documentation of his or her own personal journey through the programme.

Delivery of the intervention: PuP is a 20-24 week programme designed to be delivered in families' homes although, where there are concerns regarding practitioner safety, it can be delivered equally well in community-based clinical settings. For this study, PuP will be delivered by four organisations: PrePare, CIRCLE, Children 1st and WLDAS. Between them, they have 12 full-time trained practitioners (six located in CIRCLE, two in PrePare, two in Children 1st and two in WLDAS), trained by the developers of PuP ([name] and [name]), who will deliver the programme to fathers and families enrolled in this study.

CIRCLE is a Scottish National Charity for Vulnerable Children and Families which provides a community-based early years' and family support service to over 600 families per year, targeting the most disadvantaged families, especially those affected by parental substance misuse. It has purpose built facilities for working with parents, children and families but also provides a home visiting service for difficult-to-engage families. Circle is an established and highly regarded service, commissioned to provide family support services in Edinburgh, East, Mid and West Lothian by the Alcohol and Drug Partnerships, and is therefore an ideal organisation to deliver the intervention.

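### Objective 6 promises to have determined the intra-cluster correlation, but 24 families in one arm, in 4 agencies or under 12 practitioners, cannot estimate it with useful precision

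*Protocol*

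**What the plan says.** The protocol's Research objectives are introduced as things that will be complete at 24 months. Objective 6 begins "Determined key trial design parameters for a possible future large-scale trial" and its list includes "recruitment and retention rates and strategies, outcome measures, intra-cluster correlation and sample size". The ICC therefore stands beside sample size as a finished product of the study.

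The design behind it is as follows.

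- Research design, Part One: "we will enrol 24 fathers and their families in the PuP programme", and "The intervention will be delivered by twelve accredited PuP practitioners employed by four partner agencies".
- The intervention, Delivery of the intervention: the practitioners are "six located in CIRCLE, two in PrePare, two in Children 1st and two in WLDAS".
- Sample size justification: "A sample size, limited to a maximum of 24 families". The main reason given for this number is qualitative. Sixteen families are wanted at programme completion and 6-month follow-up, and one third is added for attrition.
- Outcome measures, Randomisation: nothing is randomised. Cluster randomisation is explored by asking service managers whether they would be willing in principle.

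The ICC is mentioned nowhere else in the protocol. No cluster level, outcome, target precision or external source is given for it.

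**The concern.** An ICC is estimated from the variation between clusters, so its precision depends mainly on how many clusters there are and on having several members in each. Four agencies give three degrees of freedom between clusters. Twelve practitioners give eleven, but with only about two families each. A sample chosen for in-depth interviews was never meant to carry this parameter. Because every enrolled family is offered PuP, clustering of post-treatment outcomes under usual care is not observed either.

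Cluster randomisation is one of the designs the protocol keeps open, and research question 11 asks which design would suit a future evaluation. If a value labelled as determined were passed to whoever sizes that trial, it could be anything from no clustering penalty to a very large one. Nothing in the objective warns the user of that.

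**Working it through.** **The plan's own figure.** 16 / (1 - 1/3) = 24 families, which matches the stated sample size exactly. The protocol gives no ICC or precision for one, so there is no ICC figure to reproduce.

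**Inputs from the protocol.** 24 families enrolled; 16 completers; 4 agencies; 12 practitioners split 6, 2, 2, 2.

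**Assumptions, because the protocol is silent.** True ICC from 0.01 to 0.20. Families per agency in proportion to practitioners: 12, 4, 4, 4 at enrolment and 8, 3, 3, 2 among completers. Two families per practitioner. Normally distributed outcome, one-way analysis-of-variance estimator.

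**Formulas.** With k clusters of size m, let F be the observed ratio of between- to within-cluster mean squares.

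- Estimate: (F - 1) / (F + m - 1)
- F is distributed as [(1 + (m - 1) x ICC) / (1 - ICC)] times an F variable with k - 1 and k(m - 1) degrees of freedom
- The estimate is zero or negative when F is 1 or less

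**Practitioners, 12 x 2, true ICC 0.05.** The multiplier is 1.05 / 0.95 = 1.105. The 2.5% and 97.5% points of F(11, 12) are 0.292 and 3.321, so the observed ratio lies between 0.322 and 3.671.

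- Lower: (0.322 - 1) / (0.322 + 1) = -0.51
- Upper: (3.671 - 1) / (3.671 + 1) = 0.57
- Chance of an estimate at or below zero: P(F(11, 12) <= 1/1.105) = 44%

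**Agencies, 12, 4, 4, 4, true ICC 0.05.** With unequal sizes, m in the estimator is replaced by (24 - (144 + 16 + 16 + 16)/24) / 3 = (24 - 8) / 3 = 5.33. Simulation gives -0.21 to 0.43, with 48% at or below zero.

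**Across assumed true ICCs.** Each cell gives the middle 95% of estimates and, in brackets, the share at or below zero.

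| Layout | 0.01 | 0.05 | 0.10 | 0.20 |
|---|---|---|---|---|
| 12 practitioners x 2 | -0.54 to 0.54 (49%) | -0.51 to 0.57 (44%) | -0.47 to 0.60 (37%) | -0.39 to 0.67 (25%) |
| Agencies 12, 4, 4, 4 | -0.21 to 0.37 (56%) | -0.21 to 0.43 (48%) | -0.20 to 0.49 (40%) | -0.19 to 0.60 (27%) |
| Agencies 6, 6, 6, 6 | -0.18 to 0.34 (56%) | -0.18 to 0.40 (47%) | -0.17 to 0.48 (38%) | -0.16 to 0.59 (25%) |
| Completers 8, 3, 3, 2 | -0.35 to 0.50 (56%) | -0.35 to 0.55 (50%) | -0.34 to 0.60 (44%) | -0.33 to 0.68 (33%) |

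Every range includes zero and reaches at least 0.34. The even split of six per agency shows that the result does not come from the assumed imbalance. The progression criteria table implies 8 practitioners rather than 12. Eight clusters of three at ICC 0.05 give -0.33 to 0.48, so that count does not help.

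**What such values would mean for sizing.** The design effect is 1 + (m - 1) x ICC. With an assumed 10 families per future cluster:

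- ICC 0: 1.0
- ICC 0.05: 1 + 9 x 0.05 = 1.45
- ICC 0.40: 1 + 9 x 0.40 = 4.6

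When the truth is 0.05, all three ICC values fall inside the sampling range of every layout in the table.

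**The case against.** The best defence is that Objective 6 does not say the ICC will be computed from these 24 families. Its list mixes quantities with decisions, such as strategies and outcome measures, which can be settled by judgement or outside evidence. The Statistical analysis section describes what the data will supply for the future sample size as "including standard deviation values to inform the sample size calculation of the future trial" and does not name the ICC. That is compatible with no intention to estimate it here. This reading is possible, but the protocol states no external source, and the verb used is a claim of determination. The defence therefore supports clearer wording and does not support leaving the text as it is.

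Three stronger readings are tempting, and the documents do not support them.

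- **The future trial will be under-sized.** The protocol never says it will compute a design effect. Harm would arise only if a zero or negative estimate were used without its interval. The protocol also places a pilot randomised trial before any full evaluation and treats cluster randomisation as only one option.
- **The statistical section is deficient because it names no ICC estimator.** A protocol commonly leaves that to the statistical analysis plan, which was not available for this review. The point here is different: no estimator can recover information that the sample does not hold.
- **The standard deviation will be misused too.** The protocol says standard deviations will inform the calculation. It does not say they will be carried forward as point values. Sizing on an upper confidence limit is one convention among several, so no change is asked for.

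**Conclusion.** The point holds in a limited form. The study can compute an ICC but cannot determine one in any sense useful for design, and a statistical analysis plan cannot change that. At an assumed true ICC of 0.05, the middle 95% of estimates spans about -0.21 to 0.43 (agencies) or -0.51 to 0.57 (practitioners), with 44% to 48% at or below zero. The conclusion does not depend on choosing 0.05.

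It rests on agency or practitioner being the cluster level, which the protocol does not define, and on a family split inferred from staffing. The design-effect figures also rest on an assumed cluster size and are illustrative only.

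Severity is minor. The main outcome is the progression criteria, none of which involves the ICC, and effectiveness is not a study aim. No participant, endpoint or go/no-go decision turns on this phrase.

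**What to change.** Remove the intra-cluster correlation from the parameters that Objective 6 says will have been determined. Add one sentence saying that any ICC for a future cluster design will be taken from external sources, over a plausible range whose source is cited, with the resulting design effects shown. Add that any estimate from this study will be reported only with its confidence interval, with the cluster level named, and will not be used alone for sizing.

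The cost is a wording change and a less ambitious objective. Recruitment, data collection and the sample size of 24 stay as they are.
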